Effect Of Secretin On Gastric
Accommodation, Emptying,
and Post-nutrient Challenge
Symptoms in Functional
Dyspepsia and Healthy Subjects

NCT# 03617861

April 19, 2019

Effect of secretin on gastric accommodation, emptying and post-nutrient challenge symptoms in functional dyspepsia and healthy subjects

Version /7, date 4/19/2019

Co-Principal Investigators: [name], Mayo Clinic Rochester

[name], Mayo Clinic Arizona

Co-investigators: [name] MD, [name] MD, [name] [name], [name]

[name], MHA, [name] BS, [name] MS,

Hypothesis: Secretin enhances gastric accommodation and reduces post-nutrient challenge symptoms without altering gastric emptying in patients with functional dyspepsia with normal baseline gastric emptying.

Specific Aims:

- 1. To compare the effects of secretin vs. saline on satiation, fasting gastric volume, gastric accommodation and emptying, and symptoms in patients with functional dyspepsia with normal gastric emptying.
- 2. To compare the effects of secretin vs. saline on satiation, fasting gastric volume, gastric accommodation and emptying, and symptoms in healthy human volunteers.
- **3.** To compare effects of secretin on satiation, fasting gastric volume, gastric accommodation and emptying, and symptoms in patients with functional dyspepsia with normal gastric emptying and in healthy human volunteers

Background

Functional dyspepsia (FD) is a very common cause of substantial morbidity, estimated to affect ten percent of the population, and manifest as abdominal pain after eating, present at least three days per week. It has been estimated that 40 percent of patients with this symptom complex consult their physician, with impact on their workplace attendance and productivity, and an economic impact in excess of 18 billion dollars in 2009 (1). Current medical treatment includes eradication of H pylori, acid suppression, prokinetic drugs, antidepressants, and psychological and alternative therapy, yet, despite this, many patients remain refractory to treatment, experiencing continued disabling symptoms (2).

Insights into the pathophysiology of this disorder provide clues suggesting possible dysfunction of the gastrointestinal hormone, secretin, and the possible therapeutic use of a secretin agonist or positive allosteric modulator (PAM) in the management of this syndrome. A prominent pathophysiologic feature of FD is defective gastric accommodation, with inadequate relaxation of the fundus of the stomach in response to eating responsible for the post-cibal pain. A key physiologic regulator of gastric accommodation is secretin. Additionally, the site of synthesis and secretion of this hormone is enteroendocrine S cells in the duodenum, a site recently described as being involved pathologically with inflammation and eosinophilia in FD (3). Secretin is believed to elicit gastric fundic relaxation through its effects on secretin receptors on vagal afferent neurons, which go on to release VIP and prostaglandins (4, 5). While these events have been well documented in animal models and healthy human subjects, there are no published data for the effectiveness of secretin in stimulating gastric accommodation in patients with FD.

Secretin and its potential role in functional dyspepsia

Insights into the pathophysiology of functional dyspepsia, with recent demonstration of inflammation with eosinophilia and mastocytosis in the duodenum (3, 6, 7), providing a possible lead toward reduced secretion of a potential mediator of post-prandial gastric accommodation, the gastrointestinal peptide hormone secretin. The dominant site of synthesis and secretion of this hormone are enteroendocrine S cells in the duodenum. Inflammation-induced damage to these cells could produce a deficiency. Since intraluminal acid is a prominent stimulant of S cell secretion, the attempts to treat functional dyspepsia with anti-secretory medications could actually exacerbate a secretin deficiency syndrome. This raises the possibility of the therapeutic use of a secretin agonist or a positive allosteric modulator of the secretin receptor for patients with functional dyspepsia.

A prominent pathophysiologic feature of functional dyspepsia is defective gastric accommodation, with inadequate relaxation of the fundus of the stomach in response to eating responsible for the postcibal pain. This was observed in 47% of 151 patients with functional dyspepsia in a Mayo Clinic study performed in the clinical practice of the PI (8). There are presently no generally effective medications to restore normal gastric accommodation, and there is only limited support, based on single-center studies, for the use of such diverse medications as clonidine, sumatriptan, and buspirone, many of which have central or vascular side effects, or acotiamide, a cholinesterase inhibitor approved for use in Japan, but not in the USA.

A key physiologic regulator of gastric accommodation is secretin. Secretin is believed to elicit gastric fundic relaxation through its effects on secretin receptors on vagal afferent neurons, which go on to release VIP and prostaglandins (4, 5). While these events have been well documented in animal models and healthy human subjects, there are no published data for the effectiveness of secretin in stimulating gastric accommodation in patients with functional dyspepsia.

We postulate that therapy that increases levels and/or effectiveness of secretin to relax the gastric fundus in FD patients will increase gastric accommodation and reduce post-cibal abdominal pain and other symptoms. This can theoretically be accomplished with a secretin agonist or a PAM increasing the biological response to physiologically-released secretin. Therefore, it is important to establish whether secretin can induce gastric accommodation in FD, supporting use of exogenous secretin, or, if the secretin response is blunted or absent, suggesting that an allosteric modulator might be important to develop for this application.

Currently, only natural secretin peptide is approved for clinical use, and is a safe and effective reagent that can only be administered parenterally for diagnostic purposes. No orally active secretin agonist or PAM has yet been reported.

Study Design

We will utilize single photon emission computed tomography (SPECT) methodology and gamma scintigraphy present in the GI laboratory of the outpatient Clinical Research Unit to study fasting gastric volumes and postprandial gastric accommodation responses and gastric emptying rates of a standardized meal in patients with functional dyspepsia and healthy subjects. Both groups will be studied twice, using crossover design, once with administration of secretin and once with placebo. This will provide each subject as his/her own control, as well as providing contrast in baseline and responsiveness to this hormone across the groups.

Rationale for Crossover design and selection of FD patients

The pathophysiology of functional dyspepsia includes:

- a. Delayed gastric emptying
- b. Accelerated gastric emptying (sometimes associated with impaired gastric accommodation)
- c. Reduced postprandial gastric accommodation
- d. Hypersensitivity to gastric mechanical distension
- e. Hypersensitivity to duodenal nutrients
- f. Duodenal inflammation
- g. Combinations of different mechanisms

Given the interest in secretin, we shall select patients with **FD and prior documentation of normal or accelerated gastric emptying and/or reduced gastric accommodation.** Given the diversity of mechanisms, the most efficient way to appraise the effects of secretin or PAM is through a crossover design.

Eligibility Criteria

Functional dyspepsia patients (n=15) and healthy subjects (n=15) aged 18-65 years will be recruited, and enrolled after providing written informed consent. The goal is to obtain the completed crossover results from 10 healthy and 10 Functional dyspepsia patients. Once that criterion is satisfied, enrollment will stop. The FD group will be identified from Mayo Clinic patients living within a 50 mile radius (Olmsted and Goodhue counties) who have symptoms consistent with this diagnosis and who have been studied and found to have normal or accelerated gastric emptying. Subjects may be involved in study activity for up to six weeks from screening date to completion of all studies. The actual study will be conducted on two separate days, each involving 3-4 hours of study. These testing visits should be scheduled one week apart, but within 4 weeks.

Male and female subjects, aged 18 to 65 years at screening, who meet the following criteria, will be eligible for enrollment. A detailed history will be obtained with validated questionnaires [including Hospital Anxiety and Depression Inventory, Functional Dyspepsia Symptom Diary, abridged Bowel Disease questionnaire (for healthy subjects only) and the long Bowel Disease (for functional dyspepsia patients only) (Zigmond & Snaith 1983, Patient-Reported Outcome Consortium's Functional Dyspepsia Working Group 2018, Talley 1990, Talley 1990)].

Inclusion criteria:

- Able to provide written informed consent prior to any study procedures and be willing and able to comply with study procedures
- No medical problems or chronic diseases that could significantly affect GI function, other than functional dyspepsia, for that group
- Body mass index of 18-40 kg/m²

- Female subjects must have negative urine pregnancy tests and must not be lactating prior to receiving study medication and radiation exposure. For females able to bear children, a hormonal (i.e., oral, implantable, or injectable) and single-barrier method, or a double-barrier method of birth control must be used throughout the study. Female subjects unable to bear children must have this documented in the medical record [i.e., tubal ligation, hysterectomy, or post-menopausal (defined as a minimum of one year since the last menstrual period)].
- Rapid or normal gastric emptying (GE) measured via scintigraphy in past 5 years for FD subjects
- Normal upper endoscopy (EGD) in past 5 years for FD subjects

Exclusion criteria:

- Significant change in symptoms since previous EGD and/or GE study for FD subjects
- Unable or unwilling to provide informed consent or to comply with study procedures
- Structural or metabolic diseases that affect the GI system
- Unable to stop acid reducers such as proton pump inhibitors, H2 blockers 3 days prior to study days
 - o May permit antacids on as needed basis but must stop 8 hours before study days
- Unable to avoid the following over-the-counter medications 48 hours prior to the baseline period and throughout the study:
 - Medications that alter GI transit or motor function including laxatives, magnesium and aluminum containing antacids, prokinetics, erythromycin, buspirone, clonidine, tricyclic antidepressants, and secretin-norepinephrine reuptake inhibitors, buproprion, benzodiazepines (, ,), anticholinergics (tricyclic antidepressants, trazodone, cyclobenzaprine, antihistamines), anti-emetics (promethazine, prochloperazine, ondansetron)
 - Analgesic drugs including NSAIDs and COX-2 inhibitors
 - NOTE: Stable doses of thyroid replacement, estrogen replacement, low-dose aspirin for cardio-protection, low stable dose antidepressants of the SSRI class, and birth control (but with adequate backup contraception, as drug interactions with birth control have not been conducted) are permissible.
- History of recent surgery (within 60 days of screening)
- Acute or chronic illness or history of illness which in the opinion of the investigator could
 pose a threat or harm to the subject or obscure interpretation of laboratory test results or
 interpretation of study data, such as frequent angina, Class III or IV congestive heart
 failure, moderate impairment of renal or hepatic function, poorly controlled diabetes, etc.

- Any clinically significant abnormalities on physical examination or laboratory abnormalities identified in the medical record, as determined by the investigator
- Acute GI illness within 48 hours of initiation of the baseline period
- Females who are pregnant or breastfeeding
- History of excessive alcohol use or substance abuse
- Participation in an investigational study within the 30 days prior to dosing in the present study
- Any other reason, which in the opinion of the investigator, would confound proper interpretation of the study

Preliminary Data

We have conducted a search of Mayo Clinic database for patients with functional dyspepsia and identified 34 potential candidates for the study:

Pharmacokinetics and Dosing of Secretin

Synthetic natural human secretin

Pharmacokinetics and Dosing of Secretin: The standard dose of secretin used in exocrine pancreatic function testing is 0.2 mcg/kg IV over 1 min. This is also the dose used most commonly for radiographic procedures. This peptide has a half-life of approximately 2-4 min, yet has been observed to elicit agonist responses at the exocrine pancreas for a much longer period of time (minutes to hours afterward).

Dosing: We will administer the secretin at 0.2 mcg/kg IV over 1 min, immediately before initiating the Ensure administration. The placebo will be similar infusion of normal saline. Participants will receive the i.v. secretin dose on 1 occasion and the i.v. placebo on 1 occasion. *IND*: Use of the medication will be as a proof of concept with pharmacodynamics measurements rather than with intention of developing secretin as a therapeutic. However, the medication is being provided by ChiRhoClin, Inc. who has requested a new IND from the FDA: the study will be conducted under the new IND number 141437.

Supply: Human Secretin for injection (16 mcg/10 ml vial) will be provided (60 vials) by ChiRhoClin, Inc, Burtonsville, MD and will be stored in and dispensed by Mayo Clinic Pharmacy. Secretin is available as a lyophilized sterile powder in 10-mL vials containing 16mcg of human secretin. The pharmacist will reconstitute with 8mL of saline for injection to yield a final concentration of 2mcg of human secretin/mL.

Randomization

[figure not shown]
The randomization schedule will be generated before the start of the study in the Mayo Clinic Section of Biomedical Statistics and Informatics, and will be given to the research pharmacist. Medications will be *stored* in a monitored, climate-controlled environment according to manufacturer's directions. Monitoring records will be available for review to ensure quality control.

Experimental Procedures

Design: We propose to measure fasting gastric volumes, and postprandial gastric accommodation responses and gastric emptying rates of a standardized meal in functional

dyspepsia patients and healthy subjects during two testing periods. Participants in each group will be randomly assigned to receive secretin or placebo at the first sitting and the opposite for the second sitting. We will also measure acute food intake (meal size) in each participant, as the total volume ingested until they reach satiation, and postprandial symptoms. The plasma levels of several neuropeptides and hormones will be measured during fasting and postprandially to provide an initial understanding of the mechanism of action of secretin on gastric volume, accommodation and satiation indices.

Gastric Accommodation Measurements; Fasting and postprandial gastric volume (GV) by single photon emission computed tomography (SPECT [9]) developed and validated

(including performance characteristics) in our lab. Using the ratio of postprandial volume over the fasting volume is a measure of the postprandial gastric accommodation. Radiation exposure listed in Appendix.

Gastric Emptying

To assess gastric emptying during the satiation test (10), the first 300 mL of Ensure® will be radiolabeled with 50

[figure not shown]
μCi of ¹¹¹In-DTPA and 2-minute duration anterior and posterior scans of the abdomen will be obtained right after the Ensure is ingested and then 15 minutes (which will be after the end of SPECT imaging) at 5 minute intervals and then through 30 minutes from first 300mL of Ensure®. Radiation exposure listed in Appendix.

Plasma Measurements Blood draws (18 cc each) will be taken during fasting (in two occasions) and postprandially (at 15, 45 and 90 minutes after starting ingestion of Ensure) during the gastric function measurements. We will measure plasma levels of GIP, pancreatic polypeptide, and glucagon-like peptide-1 (GLP-1). A blood sample for possible future DNA testing will be collected also.

GLP-1 will be measured as the biologically active GLP-1 (active and total) using a 2-site, non-competitive immunoassay based on enzyme-labeled quantification of GLP-1 detected by a fluorogenic substrate. Total **GIP** will be measured using a two-site sandwich immunoassay using a total GIP ELISA kit (Millipore Corp, Billerica, MA, USA); the antibody used specifically recognizes human GIP (1-42) and GIP (3-42), but not other forms of oxyntomodulin, GLP-1, or GLP-2. Pancreatic polypeptide will be measured (at Mayo ICL) on the same plasma samples using radioimmunoassay technique.

Satiation (11) by Ensure® nutrient drink test with ingestion (1kcal/mL, 11% fat, 73% carbohydrate, and 16% protein) at a constant rate of 30ml/min to measure volume to fullness (VTF), and MTV. This will start 30 minutes after the initial 300 mL of Ensure was ingested. Briefly, participants record their time from their first intake to when they reach 5 levels of fullness. These levels of fullness are from 1) first sensation; 2) mild satiety; 3) moderate satiety; 4) severe satiety and 5) maximum satiety. Nutrient intake is stopped when subjects reach the maximum satiety. Time and total volume consumed to maximum satiety is calculated and the time and total volume is also calculated to moderate satiety Postprandial symptoms of fullness, nausea, bloating, and pain are measured 30 minutes after the meal using 100mm horizontal visual analog scales, with the words "none" and "worst ever" anchored at each end. Before starting any gastric testing, we will assess the volunteer's current symptoms using the Functional Dyspepsia Symptom Diary and then again along with the postprandial symptoms questionnaire 30 minutes after the meal. Questionnaires used are in Appendix.

Study Schedule

Measurement/Outcomes

Participants will undergo the following tests on two separate occasions, each lasting 3-4 hours:

- Single photon emission computed tomography (SPECT) to calculate fasting gastric volume and postprandial gastric accommodation
- Gastric emptying (by scintigraphy) of Ensure after 30 minutes
- Measurement of volume to fullness (mL), maximum tolerated volume (MTV), postprandial symptoms on satiation (nutrient drink) test

Pharmacodynamic Endpoints

Comparison of the effects of secretin vs. placebo (saline) on the following gastrointestinal functions in FD patients and healthy subjects:

- Difference in fasting gastric volume
- Difference in gastric volume after the 300 mL Ensure meal for secretin vs. placebo
- Difference in gastric emptying of radiolabeled Ensure after 30 minutes
- Volume to fullness (sensation of usual postprandial fullness) and maximum tolerated volume (MTV).
- Difference in postprandial symptoms 30 minutes after ingesting maximum tolerated volume of Ensure

Sample Size Determination

Sample size assessment for primary aim to examine the *within* dyspepsia patient response when receiving Secretin versus Placebo. Sample size is based on the results of primary endpoints in the Mayo Clinic lab [data show mean \pm SD). Within 10 dyspepsia patients, assuming a two-sided paired T test (80% power, α =0.05) in this crossover trial demonstrable differences for secretin compared to placebo is **21% in fasting gastric volume**, **13.0% in**

postprandial gastric volume and 16.6% in amount of gastric retention of Ensure at 30 minutes based on the coefficients of variation observed from the Mayo Clinic laboratory of Dr. [name] in prior studies as shown in the table below.

Response	Mean	SD	Effect size detectable (absolute [% of mean], n=10 Based on cross-over design		
Fasting gastric volume, mL Post prandial gastric volume, mL	273 848	57 111	56.8mL (20.8%) 110.6mL (13.0%)		
Gastric emptying expressed as retention of Ensure at 30 mins, (%)	72	12	11.95 (16.6%)		
Volume to fullness, mL	755	330	328.5mL (43.5%)		
Maximum tolerated volume, mL	1283	400	398.5mL (31.1%)		
Peak postprandial GLP-1, pmol/L	18.8	14	13.94pmol/L (74.1%)		

Therefore the study is powered to detect clinically relevant effects of the study medication.

A similar analysis will be conducted in the healthy human volunteers based on the cross-over design, and the anticipated effect sizes that would be demonstrable in this second group is similar to that summarized above for patients with functional dyspepsia.

A subsidiary (secondary) analysis will compare the response using secretin in FD and healthy volunteers. This will be a 2 sample, unpaired analysis of the observations on secretin treatment, with ten patients in each cohort.

The table below shows the effects sizes demonstrable for the comparison between FD and health, using a 2-group analysis (unpaired analysis), again a two-sided test at α =0.05, with 80% power.

Response	Mean	SD	Effect size detectable (absolute [% of mean], n=10 Based on 2-group comparison
Fasting gastric volume, mL Post prandial gastric volume, mL	273 848	57 111	75.5mL (27.7%) 147.0mL (17.3%)
Gastric emptying expressed as retention of Ensure at 30 mins, (%)	72	12	15.9 (22.1%)
Volume to fullness, mL	755	330	437mL (57.9%)
Maximum tolerated volume, mL	1283	400	530mL (41.3%)

Peak postprandial GLP-1, pmol/L	18.8	14	18.55pmol/L (98.8%)
---------------------------------	------	----	---------------------

Statistical Methods

It is anticipated that all primary and secondary endpoints will be normally distributed. We will use parametric tests to assess study parameters. If the data are not normally distributed we will use non-parametric tests.

For the primary aim, comparison of responses in the 10 completed dyspepsia patients for secretin versus placebo, as well as the subsidiary, analogous study conducted in healthy volunteers, the analysis will be a paired test, either a paired t test or signed rank test.

For the secondary aim, comparison of 10-15 dyspepsia patients with 10-15 healthy controls for responses after receiving secretin, the analysis will be either a two-sample t test or a rank sum test.

Covariate analysis may be conducted using a regression model, including gender and BMI as covariates, since these may significantly affect gastric functions such as satiation maximum tolerated volume, and smoking and gender since this may significantly affect drug levels of secretin. It is unclear if these covariate analyses will be required given the small sample sizes (n=10 in each group)

Safety Considerations

Informed consent

A complete description of the study will be presented to each potential study participant and signed and dated informed consent will be obtained before any study specific procedures are performed.

Demographics and medical history

A medical history and review of body systems along with demographic data will be obtained for all patients during the screening period (Days -30 to -1). Data that will be recorded in the source document/CRF include gender, race, date of birth, cigarette smoking history, alcohol use, drug abuse history and concomitant medication use.

Physical examination

A physical examination will be performed during the screening period to confirm eligibility.

Concomitant medication review

A review of concomitant medications will be conducted during the screening period and at every study visit. Any medications taken by study patients or changes in dose regimens will be recorded on a Concomitant Medication CRF.

Vital signs and weight

Vital signs will be obtained in the sitting position. Body temperature (°C), respiration rate (breaths/minute) and weight will be recorded at each time point when vital signs are measured. Height (cm) will be measured at the screening visit.

Pregnancy testing

Urine pregnancy testing will be done for women of childbearing potential at screening. Urine pregnancy testing will be done on day 1 prior to randomization to study drug and placebo and at the final study visit or earlier if the patient is discontinued.

A woman of childbearing potential is defined as any female who has experienced menarche and who has not undergone successful surgical sterilization (hysterectomy, bilateral tubal ligation or bilateral oophorectomy) or is not postmenopausal [defined as amenorrhea >12 consecutive months; or women with documented plasma follicle-stimulating hormone level >35IU/mL]. Women who are using oral, implanted or injectable contraceptive hormones, an intrauterine device, barrier methods (diaphragm, condoms, spermicidal) to prevent pregnancy, practicing abstinence or where partner is sterile (e.g., vasectomy) will be considered to be of childbearing potential.

Adverse Events:

Adverse Event Grading will be in accordance with the severity grading scheme of the National Cancer Institute (NCI) Common Terminology Criteria for Adverse Events (CTCAE), Version 5.

Grade 1 Mild; asymptomatic or mild symptoms; clinical or diagnostic observations only; intervention not indicated.

Grade 2 Moderate; minimal, local or noninvasive intervention indicated; limiting age appropriate instrumental ADL.

Grade 3 Severe or medically significant but not immediately life-threatening; hospitalization or prolongation of hospitalization indicated; disabling; limiting self care ADL.

Grade 4 Life-threatening consequences; urgent intervention indicated.

Grade 5 Death related to AE.

Study Stopping Rules:

Individual:

- 1. Acute hypersensitivity reactions (CTCAE Grade 3, 4, or 5)
- 2. Severe abdominal pain, hypotension, diarrhea or vomiting requiring hospitalization (CTCAE Grade 3, 4, or 5)

General:

- 1. Development in 3 or more participants of severe abdominal pain requiring hospitalization (CTCAE Grade 3, 4, or 5)
- 2. Development in 3 or more participants of hypotension requiring i.v. hydration or hospitalization (CTCAE Grade 3, 4, or 5)
- 3. Development in 3 or more participants of diarrhea requiring i.v. hydration or hospitalization (CTCAE Grade 3, 4, or 5)

4. Development in 3 or more participants of vomiting requiring i.v. hydration or hospitalization (CTCAE Grade 3, 4, or 5)

Safety Monitoring Duration

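### The FD-versus-healthy test uses secretin-day values only, so it cannot separate a difference in response to secretin from a gap already present on placebo

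*Combined protocol and SAP*

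**What the plan says.** **The question.** Aim 3 in Specific Aims is "To compare effects of secretin on satiation, fasting gastric volume, gastric accommodation and emptying", and symptoms, in FD patients and in healthy volunteers. Aims 1 and 2 set secretin against saline. Pharmacodynamic Endpoints is introduced as "Comparison of the effects of secretin vs. placebo (saline) on the following gastrointestinal functions in FD patients and healthy subjects". Study Design says the crossover makes each subject his or her own control, as well as "providing contrast in baseline and responsiveness to this hormone across the groups". Baseline and responsiveness are thus named as two things.

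**The test.** Sample Size Determination specifies: "This will be a 2 sample, unpaired analysis of the observations on secretin treatment, with ten patients in each cohort". Statistical Methods repeats this for the secondary aim: "for responses after receiving secretin, the analysis will be either a two-sample t test or a rank sum test". The second detectable-difference table is computed for this two-group comparison.

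**Adjustment.** In Statistical Methods, "Covariate analysis may be conducted using a regression model, including gender and BMI as covariates"; smoking is also mentioned. The analysis is optional, and the placebo-day value is not among the covariates. Neither section plans a group-by-treatment test or a between-group test of secretin-minus-placebo differences.

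**The concern.** A secretin-day comparison answers whether FD patients and healthy subjects differ while on secretin. Aim 3 asks whether secretin does something different in the two groups. The two questions coincide only if the groups have equal means on placebo.

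The background section on secretin's potential role in FD says what depends on the answer. Exogenous secretin is supported if it induces accommodation in FD; the other route applies "if the secretin response is blunted or absent, suggesting that an allosteric modulator might be important to develop for this application". The paired FD test addresses an absent response. A blunted response needs a comparison with the healthy response, and this is the only planned test that makes one. Two separate paired tests do not fill the gap, because significance in one group and not in the other is not a test of the difference.

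A placebo-day gap is plausible on the protocol's own account. The background reports defective accommodation in 47% of an earlier series of 151 FD patients, and the rationale for patient selection mentions reduced accommodation as one possible basis for choosing patients. The size cannot be predicted, because the inclusion criteria ask only for "Rapid or normal gastric emptying (GE) measured via scintigraphy in past 5 years for FD subjects" and a normal endoscopy.

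**Working it through.** **1. What the planned contrast contains.** Write S and P for the secretin-day and placebo-day means.

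FD_S − H_S = (FD_P − H_P) + [(FD_S − FD_P) − (H_S − H_P)]

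The left side is what is tested. The first term on the right is the placebo-day gap; the bracket is the difference in response.

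**2. Reproducing the plan's figures.** Inputs from Sample Size Determination: n = 10 per group, two-sided alpha 0.05, 80% power, SD 57 mL (fasting volume), 111 mL (postprandial volume) and 400 mL (maximum tolerated volume). With the noncentral t distribution (18 df, noncentrality d × √(10/2)), 80% power needs d = 1.325.

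- Fasting: 1.325 × 57 = 75.5 mL (plan 75.5)
- Postprandial: 1.325 × 111 = 147.1 mL (plan 147.0)
- Maximum tolerated volume: 1.325 × 400 = 530 mL (plan 530)

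The table is arithmetically right for a secretin-day comparison. The fault lies in what is compared.

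**3. Correlation implied by the paired table.** The paired test with n = 10 needs d = 0.996. Dividing each first-table effect by 0.996 gives the SD of differences: 56.8/0.996 = 57.0, 110.6/0.996 = 111.0, and likewise 12.0, 329.8, 400.1 and 14.0. These equal the tabulated SDs up to rounding. If the tabulated SD is that of a single observation, then rho = 1 − (SD of differences/SD)²/2 = 1 − 1/2 = 0.5 for all six endpoints. The documents do not say where this comes from.

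**4. Identical secretin effect in both groups, with a placebo-day gap.** The gaps are assumed, and the two groups have equal SDs.

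| Gap (SD) | Gap, postprandial volume (mL) | Planned test rejects |
|---|---|---|
| 0 | 0 | 5.0% |
| 0.25 | 27.8 | 8.3% |
| 0.5 | 55.5 | 18.5% |
| 0.75 | 83.2 | 35.5% |
| 1 | 111 | 56.2% |

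Simulation (100,000 trials per setting; gaps 0, 0.5 and 1 SD; rho 0.5 and 0.8) agrees. It puts the test of differences at 4.9% to 5.1% throughout.

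The planned test gives the same 56.2% for a 1 SD gap with no difference in response, for no gap with a 1 SD difference in response, and for 0.5 SD of each in the same direction. A significant result does not say which occurred.

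**5. Opposing gap.** Suppose the FD response is truly 111 mL (1 SD) larger and FD starts 55.5 mL (0.5 SD) lower. The secretin-day contrast is 1.0 − 0.5 = 0.5 SD, and the planned test has 18.5% power. For the test of differences, d = 1/√(2(1 − rho)), and power is 43%, 56%, 78% and 92% at rho 0.3, 0.5, 0.7 and 0.8. With no gap the planned test has 56%, so it is the more powerful test when the gap is zero and rho is below 0.5.

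**6. Detectable difference in response after the fix.** Formula: 1.325 × SD × √(2(1 − rho)), 80% power, ten per group.

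| rho | Postprandial volume (mL) | Maximum tolerated volume (mL) |
|---|---|---|
| 0.3 | 174 | 627 |
| 0.5 | 147 | 530 |
| 0.7 | 114 | 411 |
| 0.8 | 93 | 335 |

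**The case against.** **The aim is secondary and loosely worded.** Sample Size Determination calls this analysis subsidiary, the hypothesis concerns FD only, and Aim 3 omits the comparison with saline that Aims 1 and 2 state. That limits the weight of the point. It does not rescue the test: Study Design separates baseline from responsiveness, and the endpoints are secretin-versus-placebo contrasts. The phrase in Statistical Methods could be read as change from placebo, but Sample Size Determination is explicit that the secretin-day observations are compared.

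**Masking does not arise in the blunted case.** If FD patients start lower and also respond less, the two terms have the same sign and the planned test is pushed towards rejection. This is right. Masking needs opposing signs, as in step 5. In the blunted case the fault is misattribution.

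**Accommodation is defined as a postprandial-to-fasting ratio.** The ratio adjusts for same-day fasting volume, not for the placebo-day response, and it does not apply to emptying, satiation volumes or symptoms. What stands is that scale matters: the 5% figure assumes an effect additive in mL. If secretin acts proportionally and the groups start at different levels, raw differences also depend on baseline.

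**Fasting volume is a poor example.** Secretin is given just before the meal. If the fasting scan comes earlier, there is no fasting response to compare, and a secretin-day contrast in fasting volume shows the baseline gap alone. Fasting volume is therefore left out of the last table.

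**The corrected test is not strong.** If healthy subjects respond by 110.6 mL and FD patients not at all, it has about 43%, 56% and 78% power at rho 0.3, 0.5 and 0.7. This is true. The fix corrects the question asked; it does not make ten per group adequate for blunting.

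**Conclusion.** The concern holds. The plan's only between-group test does not estimate the difference in response that Aim 3 asks about. If secretin acts identically in both groups, its chance of declaring a group difference rises from 5% with no placebo-day gap to 19% at 0.5 SD and 56% at 1 SD. In the other direction, a true response difference of 1.325 SD, for which the plan claims 80% power, would be detected 41.5% of the time against an opposing gap of 0.5 SD and 10.6% against 1 SD.

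These figures assume ten per group, equal SDs, approximate normality and an additive effect. The gap sizes are assumptions, since the documents give no FD-versus-healthy placebo-day values. The primary paired analysis in FD and its counterpart in healthy volunteers stand as planned. This should be fixed before analysis, but it does not threaten the primary result.

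**What to change.** Replace the sentence in Sample Size Determination with:

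> Each subject's secretin-minus-placebo difference will be compared between FD and healthy volunteers by a two-sample t test or rank sum test. Placebo-day values will be compared between the groups separately, as the baseline comparison.

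Make the same change in Statistical Methods, and name the scale for each endpoint (raw volume or ratio). With complete data and no period term, the t test version is equivalent to the group-by-treatment term in a mixed model; the rank sum version is not. The secretin-day comparison can remain as a descriptive summary.

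State the SD of within-subject differences, or rho, from the laboratory's earlier data, and recompute the second table from it. At rho 0.5 its figures do not change.

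**Cost.** Two sentences and one table, with no new patients or measurements. Precision is worse than the current table shows if rho is below 0.5 (174 mL instead of 147 mL for postprandial volume at rho 0.3). Statistical Methods allows 10 to 15 per group, which could include subjects with a secretin day only. They would drop out of the test of differences unless the mixed model is used.
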